#### 4.7 **BLIND DATA REVIEW**

The checking and assessment of data to revisit the proposed methods of statistical analysis for the purpose of finalizing the planned analysis prior to the database lock will be conducted. The following lists some of the aspects of analysis that would be considered:

- Checking of data for potential exclusions from ITT population;
- Precise definitions of analysis populations, especially which subjects will be included and which will be excluded;
- Handling of missing data;
- Outlier identification and specific decisions taken on how these will be handled.

The data review will be documented in agreed and signed meeting minutes, which will include a version of Listing 16.2.3 as appendix. The blind data review meeting minutes will be included in Appendix 13.1.

#### 5. **EFFICACY ANALYSES**

Efficacy analyses will be conducted for the ITT population. Where appropriate, a restricted ITT population may also be used.

Descriptive statistics will be presented for all efficacy variables by visit and treatment group.

All significance tests will be performed at the 0.05 level.

#### 5.1 GENERAL CONSIDERATIONS AND STATISTICAL/ANALYTICAL ISSUES

#### 5.1.1 **Definition of Baseline**

Unless stated otherwise, subject's Visit 2 will be considered as Baseline for statistical analyses. If subject's Visit 2 assessment is missing, the last available value on or prior to the first study dose date will be used as baseline.

#### 5.1.2 **Treatment Comparisons**

Statistical testing to compare treatment groups will be performed for the ITT population only using appropriate statistical methods, as described in the efficacy subsections below. Given the small per-treatment group sample size for the study, the resulting p-values from the statistical testing will be used for descriptive purposes only (i.e., not for inferential purposes), primarily as an aid in the clinical interpretation of the efficacy results.

#### 5.1.3 **Pooling of Centers**

As sample size per center will be small, all the centers will be pooled together for the analysis.

### 5.1.4 Multiple Comparisons/Multiplicity

Treatment comparisons will be performed at Visit 3 through Visit 8 but without adjustment for multiple comparisons as sample size is small and is not based on any power calculations. P-values will be used only for interpretation.

### 5.1.5 Examination of Subgroups

Subgroup analyses for efficacy will be performed on categories of the following measures:

- Sex
- Race

for the ITT population for the investigator-rated CAARS Total ADHD Symptom Score.

Subgroup analyses will also be carried out for

- investigator-rated CAARS inattention subscale score
- investigator-rated CAARS hyperactivity/impulsivity subscale score.

Investigator-rated CAARS inattention subscale score has 9 items (1, 9, 13, 14, 19, 21, 26, 29 and 30) and investigator-rated CAARS hyperactivity/impulsivity subscale score has 9 items (2, 4, 6, 8, 16, 18, 22, 25 and 27). These two subscales together make up the CAARS Total ADHD Symptom Score.

### 5.1.6 Methods for Handling Dropouts or Missing Data

Subjects who discontinue the study without post-randomization scores will not be included in the analysis of efficacy variables. Last observation carried forward (LOCF) technique will be used in the efficacy analysis for subjects who discontinue the study with post-randomization scores where last observation carried forward will be the last non-missing observation on scheduled or unscheduled visits.

If more than one item of a subscale is missing, the score for the subscale (and the total score) will also be considered missing. If only a single item is missing, the mean score for all other items in the subscale will be imputed as the score for the missing item.

### 5.2 PRIMARY EFFICACY ANALYSIS

The primary efficacy measure is the investigator-rated CAARS Total ADHD Symptom Score which is the sum of the Inattention and Hyperactivity/Impulsivity subscales (18 item measured on 4-point scale).

The changes from baseline to endpoint (Visit 8) in the investigator-rated CAARS Total ADHD Symptom Scores will be compared between the SPN-812V 300mg/day group and placebo using the two-sample t-test if normality assumption is satisfied.

In case of non-normality of scores, Wilcoxon rank-sum test will be used. The Hodges-Lehmann estimate and associated 95% confidence interval will be calculated for the median difference between treatments.

Tables 14.2.1.1 and 14.2.1.2 provide the primary efficacy results for ITT and restricted ITT populations respectively. Figures 14.2.1.3 and 14.2.1.4 provide visit-wise mean change from baseline in investigator-rated CAARS Total ADHD Symptom Score for the two treatments for ITT and restricted ITT populations respectively. Figures 14.2.1.5 and 14.2.1.6 provide cumulative proportion of subjects against change from baseline to the end of study (Visit 8) in investigator-rated CAARS Total ADHD Symptom Score for the two treatments for ITT and restricted ITT populations respectively. Listing 16.2.6.1 provides the investigatorrated CAARS Total ADHD Symptom Score data for the ITT population.

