### Primary Efficacy Analyses

The primary efficacy measure is the investigator-rated CAARS Total ADHD Symptom Score which is the sum of the Inattention and Hyperactivity/Impulsivity subscales (18 items rated on 4-point scale).

The changes from baseline to the endpoint in the investigator-rated CAARS Total ADHD Symptom Scores will be compared between the two treatment groups using the Wilcoxon rank-sum test or the two-sample t-test. To confirm the results (sensitivity analysis), a mixed model repeated measures (MMRM) analysis will be conducted. MMRM analysis will contain fixed effect terms for treatment, investigative site, visit, and interaction between treatment and visit. The model will include post-baseline values of the investigator-rated CAARS Total ADHD Symptom Score as the dependent variable with a random patient effect and baseline investigator-rated CAARS Total ADHD Symptom Score as a covariate and will use an unstructured covariance.

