#### 9.7.1.2.1. Primary Efficacy Analysis

The primary efficacy measure is the investigator-rated CAARS Total ADHD Symptom Score which is the sum of the Inattention and Hyperactivity/Impulsivity subscales (18 items measured on 4-point scale: 0, 1, 2, and 3).

The changes from baseline to the endpoint (visit 8) in the investigator-rated CAARS Total ADHD Symptom Scores will be compared between the two treatment groups using the Wilcoxon rank-sum test or the two-sample t-test.

To confirm the results (sensitivity analysis), a mixed model repeated measures (MMRM) analysis will be conducted. MMRM analysis will contain fixed effect terms for treatment,

investigative site, visit, and interaction between treatment and visit. The model will include post-baseline values of the investigator-rated CAARS Total ADHD Symptom Score as the dependent variable with a random patient effect and baseline investigator-rated CAARS Total ADHD Symptom Score as a covariate and will use an unstructured covariance.

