#### **10.3.** Changes to the Protocol

There are to be no changes to the protocol without written approval from the Sponsor. The protocol will be followed as written.

Any change to the protocol requires a written protocol amendment or administrative change that must be approved by the Sponsor before implementation. Amendments specifically affecting the safety of subjects, the scope of the investigation, or the scientific quality of the study require additional approval by the applicable IRBs. These requirements should in no way prevent any immediate action from being taken by the Investigator, or by the Sponsor, in the interest of preserving the safety of all subjects included in the study. If an immediate change to the protocol is felt by the Investigator to be necessary for safety reasons, the Medical Monitor must be notified promptly and the IRB for the site must be informed promptly.

Changes affecting only administrative aspects of the study do not require formal protocol amendments or IRB approval, but the IRB must be kept informed of such changes. In these cases, the Sponsor will send a letter to the IRB detailing such changes.

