#### 5.4 SENSITIVITY ANALYSIS

To confirm the results (sensitivity analysis), a mixed model repeated measures (MMRM) analysis will be conducted. MMRM analysis will contain fixed effect terms for treatment, investigative site, visit, and interaction between treatment and visit. Visit will be used as repeated measure. The model will include change from baseline of the investigator-rated CAARS Total ADHD Symptom Score as the dependent variable with a random patient effect and baseline investigator-rated CAARS Total ADHD Symptom Score as a covariate and will use an auto regressive (1) covariance.

Table 14.2.3 provides the sensitivity analysis results for the investigator-rated CAARS Total ADHD Symptom Score for the ITT population.

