#### 9.1.1 Title of a Table/Listing

The first line of the title will immediately follow the header line (i.e., no blank line in between). The title of a table/listing will be centered. The first letter of each imperative word will be capitalized. Up to 6 lines of the page are available to enter the title. (Note: There will be no blank title lines.)

The title will state the table/listing number, describe the table/listing briefly, and describe the population that is included in the table/listing, i.e.:

> Line 1 of title: Table xx.x. Line 2 of title: Main title

Line 3 of title (optional): Subtitle Line 4 of title: XXX Population

If Line 3 is not utilized, then Line 4 will be moved up.

The table/listing numbering will be consecutive, with no skipping of numbers. Up to 5 levels of numbering (i.e., xx,x,x,x,x or xx,x,x,x) are allowed. If the same table/listing is produced for multiple analysis populations (e.g., ITT Population and restricted ITT Population) or data imputations (e.g., Observed Data and LOCF Data), the resulting multiple tables/listings should share the same table/listing number, except for the last level, which will be consecutively numbered 1, 2, 3,..., t where t is the total number of tables/listings generated (e.g., 4.2.1 for ITT Population and 4.2.2 for restricted ITT Population).

For numeric variables, the appropriate unit will be added to the column heading. For frequency tables, only those categories for which there is at least one subject represented in one or more groups should be included. Within data listings, subjects will be ordered by treatment, investigator number, subject number, randomization number, visit, visit date and time of collection (if available).

Verbose titles should be avoided. In the case where a title line is too wide for the page, then the title line will wrap on to the next line, and all subsequent lines will increment by one.

If there is stratification or subgrouping of the population (e.g., Sex) with summaries to be presented for each subgroup on a separate page, the subgrouping label on a page (e.g., Males) will appear, left-aligned with the body of the table/listing, on the line immediately below the last title line.

There will be a solid horizontal line across the page immediately below the last title line (or the subgroup label, if present), as wide as the body of the table/listing.

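### The primary CAARS comparison leaves out baseline as a covariate, and the MMRM meant to confirm it is not stated to use observed data

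*SAP*

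**What the plan says.** **Primary comparison.** In SAP 5.2, change from baseline to Visit 8 in the investigator-rated CAARS total "will be compared between the SPN-812V 300mg/day group and placebo using the two-sample t-test if normality assumption is satisfied". If normality fails, a Wilcoxon rank-sum test with a Hodges-Lehmann estimate and 95% interval is used. Protocol 9.7.1.2.1 has the same pair of tests: changes "will be compared between the two treatment groups using the Wilcoxon rank-sum test or the two-sample t-test". The synopsis agrees. SAP 5.3.1, 5.3.3 and 5.3.4 follow the same pattern for week 1, Visits 4 to 8 and the self-rated scale.

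**Baseline.** CAARS is taken at Visit 2 (SAP Table 1), and a baseline efficacy assessment is a condition of ITT membership (SAP 4.2). The MMRM in SAP 5.4 includes "baseline investigator-rated CAARS Total ADHD Symptom Score as a covariate".

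**Missing data.** SAP 5.1.6: "Last observation carried forward (LOCF) technique will be used in the efficacy analysis for subjects who discontinue the study with post-randomization scores". No analysis is exempted. SAP 5.4 sets out the MMRM's fixed effects, dependent variable, covariate and covariance, but not whether missing visits stay missing. It names one output: "Table 14.2.3 provides the sensitivity analysis results for the investigator-rated CAARS Total ADHD Symptom Score for the ITT population". Observed data are mentioned only in the numbering rules of SAP 9.1.1, which allow for different "data imputations (e.g., Observed Data and LOCF Data").

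**The concern.** There are two separate points.

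1. Baseline enters the primary comparison only by subtraction. That is the most precise use of it only when the slope of the Visit 8 score on baseline is 1. The plan already treats baseline as worth modelling in the sensitivity analysis, yet the headline estimate does not use it that way. Randomization keeps the unadjusted test valid, so the cost is precision.

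2. Under SAP 3.1.2 and 3.1.3, a subject who cannot tolerate the starting dose leaves the study and is assessed on leaving. If that assessment is obtained, the subject meets the ITT definition. LOCF then lets a score taken after about one week at 150 mg/day stand as a Visit 8 result in the 300 mg/day group. The MMRM is the planned confirmation, but it can show how far LOCF drives the result only if it is fitted to observed scores. Fitted to filled-in scores, it would agree with LOCF by construction and look like corroboration.

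Safety is the primary objective, and SAP 5.1.2 makes efficacy p-values descriptive. The reader of this proof-of-concept study is left with the effect estimate and its interval, so their precision and their dependence on LOCF matter.

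**Working it through.** **Inputs from the documents.** About 25 subjects per arm (SAP 3.2) and 20% dropout (Protocol 7 and 9.2). The plan's one sizing figure reproduces: 50 × (1 − 0.20) = 40 completers, or about 5 leavers per arm. The documents give no SD, correlation, effect size or dropout timing, so those below are assumptions.

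**1. Precision gained from the covariate.** Let ρ be the baseline-to-Visit 8 correlation and k the baseline SD divided by the Visit 8 SD. In units of the squared Visit 8 SD, the variance is 1 + k² − 2ρk for change and 1 − ρ² for ANCOVA. The large-sample ratio is (1 − ρ²)/(1 + k² − 2ρk). Estimating the slope with 50 subjects multiplies this by 1 + 1/46. For example, at k = 1 and ρ = 0.5: 0.75/1.00 = 0.75, and 0.75 × 1.0217 = 0.77. Half-widths of the 95% CI assume a Visit 8 SD of 9 and no dropout, with t on 48 df (change) or 47 df (ANCOVA).

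| k | ρ | Ratio, large sample | Ratio, 25 per arm | Half-width: change → ANCOVA (points) |
|---|---|---|---|---|
| 1 | 0.3 | 0.65 | 0.66 | 6.1 → 4.9 |
| 1 | 0.5 | 0.75 | 0.77 | 5.1 → 4.5 |
| 1 | 0.7 | 0.85 | 0.87 | 4.0 → 3.7 |
| 0.7 | 0.3 | 0.85 | 0.87 | 5.3 → 4.9 |
| 0.7 | 0.5 | 0.95 | 0.97 | 4.6 → 4.5 |
| 0.7 | 0.7 | 1.00 | 1.02 | 3.7 → 3.7 |

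With ANCOVA applied to LOCF data (simulated, 5 leavers per arm, leaving at week 1 or spread over weeks 1 to 5), the ratios are 0.67, 0.76-0.77, 0.87 (k = 1) and 0.87, 0.97, 1.02-1.03 (k = 0.7).

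**2. What LOCF can do to the estimate.** Assume mean improvements of 12 (active) and 6 (placebo), a true difference of 6. Let a and p be the week-1 leavers on active and placebo, and f the share of their own arm's change that they have reached. Then:

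LOCF difference = 6 − (1 − f)(12a − 6p)/25.

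At f = 0.44 with (a, p) = (5, 0): 6 − 0.56 × 60/25 = 4.66.

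| (a, p) | f = 0.44 |
|---|---|
| (5, 0) | 4.66 |
| (5, 5) | 5.33 |
| (1, 1) | 5.87 |
| (2, 4) | 6.00 |
| (1, 3) | 6.13 |
| (0, 5) | 6.67 |

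For f from 0.25 to 0.60, (5, 0) gives 4.20 to 5.04 (−30% to −16%) and (0, 5) gives 6.90 to 6.48 (+15% to +8%). The break-even is p = 2a for any f, so under these assumptions the difference shrinks only when placebo leavers number fewer than twice the active leavers.

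**3. Whether the MMRM would show it.** Once every visit is filled in, the model's Visit 8 contrast is the difference in mean carried-forward change, adjusted with the model's own baseline slope. A 500-trial simulation with a random subject effect plus AR(1) confirmed this equality to rounding error. In 20,000 simulated trials (ρ = 0.5, k = 1, exchangeable visits, known covariance, no site terms):

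| Leavers (a, p) | ANCOVA on LOCF | MMRM on LOCF-filled data | MMRM on observed data |
|---|---|---|---|
| (5, 0) | 4.65 | 4.65 | 6.00 |
| (0, 5) | 6.66 | 6.66 | 6.00 |

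The observed-data value of 6 follows from simulating leavers on their arm's trend, which is one estimand. Precision is not assured: with 5 leavers per arm, the observed-data MMRM's variance relative to the LOCF t-test was 0.80-1.04 (k = 1) and 1.04-1.22 (k = 0.7), and 0.71-1.27 over all correlation patterns tried.

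**The case against.** The case for leaving the plan alone is substantial. Safety is the primary objective, the sample size has no statistical basis, and efficacy p-values are descriptive. The t-test is unbiased, and a baseline-adjusted Visit 8 contrast is already available from the MMRM. The gain in precision needs favourable inputs: requiring CGI-S of 4 or more may narrow the baseline spread, and at k = 0.7 with ρ of 0.5 or more almost nothing is gained. Most statisticians would take an MMRM to mean observed data. The table shells are separate documents (SAP 10) and may name the data type, and the blind data review (SAP 4.7) may revisit missing data. Restricted ITT tables and discontinuation reasons by arm are also planned. Grouping dose-reduced subjects with the 300 mg/day arm is an explicit rule, and exit assessments are not guaranteed, so the number of week-1 values carried forward may be small.

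Much of this stands. The size of either effect cannot be known from the documents, and the second point alone is close to a clarification. It does not remove the concern. The MMRM's adjusted contrast is a sensitivity result that may be less precise than the headline. The usual reading of MMRM is convention, while SAP 5.1.6 as written covers it. The blind data review has settled nothing yet. Restricted ITT drops early leavers but selects on events after randomization.

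**Conclusion.** The concern holds on both points and should be acted on; neither makes the planned test invalid.

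- **Baseline.** With 25 per arm, adjustment changes the variance by anything from a fall of about a third (ρ = 0.3, equal SDs) to a rise of 2-3% (ρ = 0.7, SD ratio 0.7). The possible gain is far larger than the possible loss.
- **LOCF and the MMRM.** The plan does not say that the MMRM uses observed data, so it may not be a check on LOCF. LOCF can move the estimate either way: −30% to +15% in the one-sided cases examined, and about 2% with one week-1 leaver per arm at f = 0.44.

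Confidence is medium. The wording is clear, but every magnitude rests on assumed correlations, SDs, effects and dropout patterns.

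**What to change.** 1. In SAP 5.2, make the headline estimate the Visit 8 difference in change from an ANCOVA with treatment and baseline investigator-rated CAARS, on the same ITT data, with its 95% CI. Do likewise in SAP 5.3.1, 5.3.3 and 5.3.4, using the self-rated baseline for the self-rated scale. Keep the t-test/Wilcoxon with Hodges-Lehmann as a check, since ANCOVA relies on a linear model.
2. State in SAP 5.4 that the MMRM uses observed scores, not carried-forward ones. It stays a sensitivity analysis: it assumes missing at random, targets a different estimand and may be less precise.
3. Report by arm how many Visit 8 values are carried forward, and how many of these come from week 1.

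**Cost.** No new data. Items 2 and 3 need SAP wording only. Item 1 also needs a matching change to Protocol 9.7.1.2.1 and the synopsis, because Protocol 10.3 states: "Any change to the protocol requires a written protocol amendment or administrative change that must be approved by the Sponsor before implementation". All of it should be done before database lock. The statistical price of item 1 is about 2-3% in variance if baseline adds nothing beyond subtraction.

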#### 5.3 SECONDARY EFFICACY ANALYSES

For the analysis of secondary efficacy variables, no statistical adjustment to the level of significance will be made for multiple endpoints and/or multiple comparisons.

The secondary efficacy analyses for various secondary efficacy measures are as follows.

#### 5.3.1 Investigator-Rated CAARS Total ADHD Symptom Score (150mg)

Initial efficacy of SPN-812V starting dose (150 mg/day) when compared to placebo as measured by changes in the investigator-rated CAARS Total ADHD Symptom Score from baseline at week 1 of treatment with starting dose will be analyzed with two-sample t-test if normality assumption is satisfied.

In case of non-normality of scores, Wilcoxon rank-sum test will be used. The Hodges-Lehmann estimate and associated 95% confidence interval will be calculated for the median difference between treatments.

Table 14.2.2.1 provides the secondary efficacy results for ITT population for the investigatorrated CAARS Total ADHD Symptom Score at week 1.

#### 5.3.2 Global Improvement (CGI-I)

Actual CGI-I scores at each post-baseline visit and endpoint will be compared among treatment groups using two-sample t-test if normality assumption is satisfied.

In case of non-normality of scores, Wilcoxon rank-sum test will be used. The Hodges-Lehmann estimate and associated 95% confidence interval will be calculated for the median difference between treatments.

Tables 14.2.2.2.1 and 14.2.2.2.2 provide secondary efficacy results for CGI-I for the ITT and restricted ITT populations. Tables 14.2.2.2.3 and 14.2.2.2.4 provide the number and percentage of subjects with CGI-I < 3 at the end of study (EOS) for the two treatment groups for the ITT and restricted ITT populations respectively. Listing 16.2.6.2.1 provides CGI-S and CGI-I data for the ITT population.

#### 5.3.3 Investigator-Rated CAARS Total ADHD Symptom Score (300mg)

The changes from baseline in the investigator-rated CAARS Total ADHD Symptom Scores will be compared between the two treatment groups for the Visit 4, 5, 6, 7 and 8 using the two-sample t-test if normality assumption is satisfied.

In case of non-normality of scores, Wilcoxon rank-sum test will be used. The Hodges-Lehmann estimate and associated 95% confidence interval will be calculated for the median difference between treatments at Visits 4, 5, 6, 7 and 8.

Tables14.2.2.3.1 and 14.2.2.3.2 provide the secondary efficacy results for ITT and restricted ITT populations for the investigator-rated CAARS Total ADHD Symptom Scores at Visits 4, 5, 6, 7 and 8. Listing 16.2.6.1 provides the investigator-rated CAARS Total ADHD Symptom Score data for the ITT population.

#### 5.3.4 **Self-Rated CAARS Total ADHD Symptom Score**

The changes from baseline at endpoint (Visit 8) in the self-rated CAARS Total ADHD Symptom Scores will be compared between the SPN-812V 300mg/day group and placebo using the two-sample t-test if normality assumption is satisfied.

In case of non-normality of scores, Wilcoxon rank-sum test will be used. The Hodges-Lehmann estimate and associated 95% confidence interval will be calculated for the median difference between treatments.

Table 14.2.2.4 provides the secondary efficacy results for ITT population for the self-rated CAARS Total ADHD Symptom Scores. Listing 16.2.6.2.2 provides the self-rated CAARS Total ADHD Symptom Score data for the ITT population.

